5.3.5 Schedule of Assessments

Schedule of Assessments are provided in Table 2 (Q1W dosing) and Table 3 (Q2W dosing).

Visit windows are included. The projection of visit days within each cycle must be made from Day 1 of the respective cycle. Furthermore, each new cycle must be initiated as soon as possible after completion of the previous cycle to maintain the dosing schedule.

All individual assessments are to be performed on or about the indicated visit day (i.e., ± 2 days) unless otherwise stated. All efforts should be made to perform assessments as close as possible to the scheduled time points.

Confidential Page 42 of 156

Table 2 Schedule of Assessments: Q1W Dosing

Pre-Treatment Period						Treatment Period ¹						Post-Treatn	nent Period ²				
	Screening			Cycle 1	l			Су	cle 2, 4,	6 etc.		(Cycle 3,	5, 7 etc		EOT	1M FUP
Day within Cycle Visit Window (± days)	D-14 to D-1	D1	D3	D8 (±2)	D15 (±2)	D22 (±2)	D1 (±2)	D8 (±2)	D15 (±2)	D22 (±2)	End of Cycle	D1 (±2)	D8 (±2)	D15 (±2)	D22 (±2)	≤ 10 d from the decision of trial treatment withdrawal	1 month after last dose of trial treatment (30+7d)
Informed Consent ³	X																
Baseline Characteristics ⁴ /Eligibility	X	X															
Safety Assessments																	
Medication/Procedure Survey	X	X	X	X	X	X	X	X	X	X	X	X	X	X	X	X	X
(S)AE Survey and Reporting	X	X	X	X	X	X	X	X	X	X	X	X	X	X	X	X	X
DLT Evaluation ⁵ Part 1 only		X	X	X	X	X	C2 only										
Vital Signs and Body Measurements	X	X		X	X	X	X	X	X	X		X	X	X	X	X	X
ECOG PS ⁶	X	X^6					X					X				X	X
Physical Examination ⁶	X	X^6					X					X				X	X
ECG ⁷	X															X	
ECHO or MUGA scan ⁸	X															X	
Safety blood samples ^{6,9}	X	X ⁶	X	X	X	X	X		X			X		X		X	X
Urinalysis ^{6,9}	X	X^6			X		X					X				X	X
Pregnancy Test	X															X	
Complement Panel ¹⁰ Part 2 only		X															
Disease Assessments																	
Disease Status Evaluation by CT/ MRI ^{11,12}	X										X					X^{12}	X^{12}
Tumor Marker Evaluation, if applicable ¹³	X										X					X	X
Archival Tumor Tissue ¹⁴ Part 1: Submit if available (optional)	X																
Additional Assessments																	
PK Samples ¹⁵		X	X	X	X	X	X	X	X	X		X	X	X	X	X	X
ADA Sample		X					C2 only					X				X	X
Skin Biopsy ¹⁶	X			X	X		-										
Tumor Biopsy ¹⁷																	
Part 1: Optional	X										C2 only						
Part 2: Required																	
Biomarker Blood Sample ¹⁸	X										C2 only					X	
Trial Treatment																	
Pan-HER Premedication ¹⁹		X		X	X	X	X	X	X	X		X	X	X	X		
Pan-HER Infusion		X		X	X	X	X	X	X	X		X	X	X	X		
Post-Infusion Monitoring		X		X	X	X	X	X	X	X		X	X	X	X		

Abbreviations (in alphabetical order): ADA, anti-drug antibody; C, Cycle; CT, computed tomography; D/d, day(s); DLT, dose-limiting toxicity; EOT, End of Treatment; ECG, electrocardiogram; ECHO, echocardiogram; ECOG PS, Eastern Cooperative Oncology Group performance status; MRI, magnetic resonance imaging; MUGA, multi-gated acquisition; 1M FUP, 1-Month Follow-up; PK, pharmacokinetic; (S)AE, (serious) adverse event

Confidential Page 43 of 156

- 1) The treatment period continues until the patient is withdrawn from Pan-HER.
- 2) Applicable for Part 2 only: After the 1M FUP Visit, the Investigator will make every effort to obtain follow-up information on response assessment and/or OS every 2 months. Response assessment follow-up is required in the event of an ongoing SD, PR or CR at the 1M FUP Visit, until PD or another therapeutic intervention is initiated. Survival follow-up is required until death, withdrawal of consent, or termination of the trial. This continued follow-up does not require an in-person visit at the trial site, but may be obtained by collection of data/documentation.
- 3) Informed consent may be obtained outside the 14-day screening period prior to C1/D1, but is recommended to be obtained no earlier than 4 weeks prior to the planned C1/D1.
- 4) Screening assessments/baseline characteristics include demographics, medical history, tumor histology, mutation status, extent of disease, prior anti-cancer treatment etc.
- 5) DLT evaluation, Applicable for Part 1 only: DLTs are reported during Cycle 1 with final assessment 7 days after the last dose of Cycle 1 or prior to dosing on C2/D1.
- 6) Does not need to be performed on C1/D1 if performed during screening ≤ 7 days from C1/D1.
- 7) In addition to the scheduled timepoints, an ECG should be performed in the event of cardiac symptoms.
- 8) In addition to the scheduled timepoints, an ECHO/MUGA should be performed in the event of cardiac symptoms.
- 9) Local laboratory results must be available and assessed prior to each Pan-HER infusion for all infusions during Cycle 1, and for every second infusion from Cycle 2 onwards. Refer to Section 8.2.9 for further details
- 10) Complement sampling, Applicable for Part 2 only, will be done C1/D1 and in the event of an IRR. Refer to Section 8.2.10 for further details.
- 11) CT or MRI imaging schedule and conditions, applying to all cohorts:
 - A CT/MRI performed within 28 days prior to C1/D1 can be used for evaluation of eligibility and as baseline scan, provided that the CT/MRI has been performed according to the clinical trial protocol requirements.
 - The first CT/MRI assessment for response is done at the end of Cycle 2 and thereafter repeated at the end of every second cycle (in the week prior to Day 1 of the next cycle).
 - In the event of suspected PD, a CT/MRI is to be performed as soon as possible.
 - In the event of CR/PR, a confirmatory CT/MRI is to be performed 28 (+7) days after the first assessment of CR/PR.
- 12) A CT/MRI at EOT should only be performed if the previous CT/MRI has been performed >3 weeks before; a CT/MRI scan at 1M FUP should only be performed if no CT/MRI documents disease progression before or at EOT.
- 13) Tumor marker evaluation to include tumor markers that are part of the trial site standard practices as indicated by tumor type, if applicable.
- 14) Archival tumor tissue, **applicable for patients in Part 1 only if tissue is available**: To be assessed locally, preferably by immunohistochemistry (IHC). Does not need to be repeated if EGFR and HER2 status have been assessed previously and the pathology report is available to document findings.
- 15) Extended PK sampling for PK profiling will be done starting C1/D1 and C1/D22. Refer to Table 11 for further details.
- 16) Skin biopsy: All patients enrolled will undergo skin biopsies. Sample is to be obtained during screening after patient eligibility has been confirmed. Sampling is to be repeated Cycle 1/Day 8 (prior to dosing) and Cycle 1/Day 15 (prior to dosing).
- 17) Tumor biopsy, **Optional for patients in Part 1. Required for all patients in Part 2:** To be assessed centrally. Tumor biopsy is to be performed after patient eligibility has been confirmed. Archival tissue may be accepted at screening if suitable for central analysis. Sampling is repeated at the end of Cycle 2 or upon PD, whichever occurs first. Refer to **Section 8.7** for further details.
- 18) Biomarker blood sample: To be obtained during screening after patient eligibility has been confirmed. Sampling is to be repeated at the end of Cycle 2 or upon PD, whichever occurs first, and at EOT.
- 19) Premedication: For Part 1, premedication is mandatory prior to each dose of Pan-HER. For Part 2, premedication is mandatory prior to each dose of Pan-HER during Cycle 1. In Part 2, premedication may be withdrawn after Cycle 2 on a patient-by-patient basis, if the patient is without evidence of IRRs. Refer to Section 7.2.1 for details.

Confidential Page 44 of 156

Table 3 Schedule of Assessments: Q2W Dosing

Pre-Treatment Period			Treatment Period ¹									Post-Treatr	Post-Treatment Period ²	
	Screening		(Cycle 1	1		C	ycle 2, 4,	6 etc.	Cycle 3	5, 5, 7 etc.	EOT	1M FUP	
Day within Cycle Visit Window (± days)	D-14 to D-1	D1	D3	D8 (±2)	D15 (±2)	D22 (±2)	D1 (±2)	D15 (±2)	End of Cycle	D1 (±2)	D15 (±2)	≤ 10 d from the decision of trial treatment withdrawal	1 month after last dose of trial treatment (30+7d)	
Informed Consent ³	X													
Baseline Characteristics ⁴ /Eligibility	X	X												
Safety Assessments														
Medication/Procedure Survey	X	X	X	X	X	X	X	X	X	X	X	X	X	
(S)AE Survey and Reporting	X	X	X	X	X	X	X	X	X	X	X	X	X	
DLT Evaluation ⁵ Part 1 only		X	X	X	X	X	C2 only							
Vital Signs and Body Measurements	X	X		X	X	X	X	X		X	X	X	X	
ECOG PS ⁶	X	X^6					X			X		X	X	
Physical Examination ⁶	X	X^6					X			X		X	X	
ECG ⁷	X											X		
ECHO or MUGA scan ⁸	X											X		
Safety blood samples ^{6,9}	X	X^6	X	X	X	X	X	X		X	X	X	X	
Urinalysis ^{6,9}	X	X^6			X		X			X		X	X	
Pregnancy Test	X											X		
Complement Panel ¹⁰ Part 2 only		X												
Disease Assessments														
Disease Status Evaluation by CT/ MRI ^{11,12}	X								X			X ¹²	X ¹²	
Tumor Marker Evaluation, if applicable ¹³	X								X			X	X	
Archival Tumor Tissue ¹⁴	X													
Part 1: Submit if available (optional)	Λ													
Additional Assessments														
PK Samples ¹⁵		X	X	X	X	X	X	X		X	X	X	X	
ADA Sample		X					C2 only			X		X	X	
Skin Biopsy ¹⁶	X			X	X									
Tumor Biopsy ¹⁷	X								C2					
Part 1: Optional / Part 2: Required	Λ								C2 only					
Biomarker Blood Sample ¹⁸	X								C2 only			X		
Trial Treatment														
Pan-HER Premedication ¹⁹		X			X		X	X		X	X			
Pan-HER Infusion		X			X		X	X		X	X			
Post-Infusion Monitoring		X			X		X	X		X	X			

Abbreviations (in alphabetical order): ADA, anti-drug antibody; C, Cycle; CT, computed tomography; D/d, day(s); DLT, dose-limiting toxicity; EOT, End of Treatment Visit; ECG, electrocardiogram; ECHO, echocardiogram; ECOG PS, Eastern Cooperative Oncology Group performance status; MRI, magnetic resonance imaging; MUGA, multi-gated acquisition; 1M FUP, 1-Month Follow-up Visit; PK, pharmacokinetic; (S)AE, (serious) adverse event

Confidential Page 45 of 156

- 1) The treatment period continues until the patient is withdrawn from Pan-HER
- 2) Applicable for Part 2 only: After the 1M FUP Visit, the Investigator will make every effort to obtain follow-up information on response assessment and/or OS every 2 months. Response assessment follow-up is required in the event of an ongoing SD, PR or CR at the 1M FUP Visit, until PD or another therapeutic intervention is initiated. Survival follow-up is required until death, withdrawal of consent, or termination of the trial. This continued follow-up does not require an in-person visit at the trial site, but may be obtained by collection of data/documentation
- 3) Informed consent may be obtained outside the 14-day screening period prior to C1/D1, but is recommended to be obtained no earlier than 4 weeks prior to the planned C1/D1
- 4) Screening assessments/baseline characteristics include demographics, medical history, tumor histology, mutation status, extent of disease, prior anti-cancer treatment etc.
- 5) DLT evaluation, Applicable for Part 1 only: DLTs are reported during Cycle 1 with final assessment 7 days after the last dose of Cycle 1 or prior to dosing on C2/D1
- 6) Does not need to be performed on C1/D1 if performed during screening \leq 7 days from C1/D1
- 7) In addition to the scheduled timepoints, an ECG should be performed in the event of cardiac symptoms
- 8) In addition to the scheduled timepoints, an ECHO/MUGA should be performed in the event of cardiac symptoms
- 9) Local laboratory results must be available and assessed prior to each Pan-HER infusion for all infusions during Cycle 1, and for every second infusion from Cycle 2 onwards. Refer to **Section 8.2.9** for further details
- 10) Complement sampling, Applicable for Part 2 only, will be done C1/D1 and in the event of an IRR. Refer to Section 8.2.10 for further details
- 11) CT or MRI imaging schedule and conditions, applying to all cohorts:
 - A CT/MRI performed within 28 days prior to C1/D1 can be used for evaluation of eligibility and as baseline scan, provided that the CT/MRI has been performed according to the clinical trial protocol requirements
 - The first CT/MRI assessment for response is done at the end of Cycle 2 and thereafter repeated at the end of every second cycle (in the week prior to Day 1 of the next cycle)
 - In the event of suspected PD, a CT/MRI is to be performed as soon as possible
 - In the event of CR/PR, a confirmatory CT/MRI is to be performed 28 (+7) days after the first assessment of CR/PR
- 12) A CT/MRI at EOT should only be performed if the previous CT/MRI has been performed >3 weeks before; a CT/MRI scan at 1M FUP should only be performed if no CT/MRI documents disease progression before or at EOT
- 13) Tumor marker evaluation to include tumor markers that are part of the trial site standard practices as indicated by tumor type, if applicable
- 14) Archival tumor tissue, **applicable for patients in Part 1 only if tissue is available**: To be assessed locally, preferably by immunohistochemistry (IHC). Does not need to be repeated if EGFR and HER2 status have been assessed previously and the pathology report is available to document findings
- 15) Extended PK sampling for PK profiling will be done starting C1/D1 and C2/D1. Refer to Table 11 for further details
- 16) Skin biopsy: All patients enrolled will undergo skin biopsies. Sample is to be obtained during screening after patient eligibility has been confirmed. Sampling is to be repeated Cycle 1/Day 8 and Cycle 1/Day 15 (prior to dosing)
- 17) Tumor biopsy, **Optional for patients in Part 1. Required for all patients in Part 2:** To be assessed centrally. Tumor biopsy is to be performed after patient eligibility has been confirmed. Archival tissue may be accepted at screening if suitable for central analysis. Sampling is repeated at the end of Cycle 2 or upon PD, whichever occurs first. Refer to **Section 8.7** for further details
- 18) Biomarker blood sample: To be obtained during screening after patient eligibility has been confirmed. Sampling is to be repeated at the end of Cycle 2 or upon PD, whichever occurs first, and at EOT. For those timepoints where both a blood sample and a tumor biopsy are to be obtained, blood sample to be collected first.
- 19) Premedication: For Part 1, intensive prophylaxis, as defined herein, on a mandatory basis is required to reduce the risk of IRRs and oropharyngeal mucositis. For Part 2, prophylaxis is mandatory during Cycle 1 and Cycle 2. Thereafter, if the patient is without evidence of IRRs or mucositis, the Investigator may choose to withdraw related medications with subsequent dosing. Refer to **Sections 7.2.1** and **7.2.2** for details

Confidential Page 46 of 156

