5.3.1 Screening

When the trial site identifies a patient suitable for screening, the Sponsor or designee should be contacted to ensure that a cohort is open for inclusion. Once confirmed, the patient may be approached for informed consent. Screening activities may begin only once written informed consent has been obtained.

All patients giving informed consent to participate in the trial will receive a unique patient number. This number is composed of a five-digit prefix (which identifies the country and site), and a three-digit number, allocated sequentially starting from 001 for the first patient screened at the site, 002 for the second patient screened, etc.

The trial site staff must complete a Screening and Allocation Form, stating the allocated patient number along with the planned dates of screening and first scheduled Pan-HER administration (Cycle 1/Day 1, in the following C1/D1). The planned date of C1/D1 will need to be agreed upon in collaboration with the Sponsor or designee for the dose-escalation cohorts in order to ensure adequate time between dosing of the first patient and dosing of any subsequent patients within each cohort. The completed Screening and Allocation Form will then be sent to the Sponsor or designee prior to or on the day of Screening.

All screening activities must be performed within 14 days prior to C1/D1, unless otherwise specified. Individual screening assessments may be repeated prior to C1/D1, if justified and documented by the Investigator.

Once eligibility has been confirmed in accordance with the inclusion and exclusion criteria (Sections 6.1 and 6.2, respectively), the Screening and Allocation Form will be fully completed and signed by the Investigator and resent to the Sponsor or designee. Sponsor or designee will approve each patient for start of treatment. A copy of the fully executed Screening and Allocation Form will be returned to the trial site for archiving. This form documents the allocated dose and schedule of Pan-HER.

Furthermore, once eligibility is confirmed:

- All patients in Part 1 and 2 will have a blood sample taken for exploratory biomarker analysis
- All patients in Part 1 and 2 will have a skin biopsy performed
- Patients included in Part 1 of the trial and consenting to the optional tumor biopsy procedure
 will have a tumor biopsy performed, unless it is confirmed that suitable archival tissue is
 available for central analysis.

Confidential Page 40 of 156

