6.2 Exclusion Criteria

Patients meeting any of the following criteria will not be permitted to enter the trial:

- 1. Any antineoplastic agent for the primary malignancy (standard or investigational) without delayed toxicity within 4 weeks or 5 plasma half-lives, whichever is shortest, prior to C1/D1 except:
 - Nitrosoureas and mitomycin C within 6 weeks prior to C1/D1
- 2. Part 2 ONLY: Radiotherapy against target lesions within 4 weeks prior to C1/D1, unless there is documented progression of the lesion following the radiotherapy

Note: Radiotherapy for pain control against non-target lesions is allowed, as long as it does not influence bone marrow function.

- 3. Immunosuppressive or systemic hormonal therapy (> 10 mg daily prednisone equivalent) within 2 weeks prior to C1/D1 with the exception of the following allowed therapies:
 - a. Hormonal therapy (e.g., Megace) for appetite stimulation
 - b. Nasal, ophthalmic, inhaled, and topical glucocorticoid preparations
 - c. Hormone replacement therapy at standard doses for end-organ failure
 - d. Steroid therapy as prophylaxis for contrast reactions
 - e. Intra-articular steroid injections
 - f. Hormonal therapy for ovarian suppression*, hormonal contraceptive therapy, postmenopausal hormone replacement therapy (HRT)
 - g. Gonadotropin-releasing hormone (GnRH) analogs in patients with prostate cancer*
 - h. Low-dose maintenance steroid therapy for other conditions (excluding steroid tapers for brain edema/metastases/radiation)
 - i. Higher dose steroid therapy for treatment of an acute intercurrent illness in patients with stable disease or an ongoing response. In such situations, study drug treatment should be interrupted for the duration of immunosuppressive therapy
 - *Patients must have been on a stable dose for at least 3 months prior to study start, and if continuing must remain on the stable dose while receiving study treatment (i.e., such treatment will not be considered as systemic hormonal therapy for the purpose of study eligibility).
- 4. Use of hematopoietic growth factors within 2 weeks prior to C1/D1
- 5. Active second malignancy or history of another malignancy within the last 3 years, with the exception of:
 - a. Treated, non-melanoma skin cancers

Confidential Page 49 of 156

- b. Treated carcinoma in situ of the breast or cervix
- c. Controlled, superficial carcinoma of the urinary bladder

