21.6 Protocol Amendment 6 dated 14-Jun-2018

- Reintroduced Q1W dosing in Part 1 dose-escalation (previously halted with Amendment 3); all current and future patients to be treated under the prophylaxis and infusion duration conditions outlined in Amendment 5.
- With reintroduction of Q1W dosing in Part 1, separate dose-escalation cohorts will be entered to assess the safety and tolerability of Pan-HER when administered either Q1W or Q2W; potential doses for evaluation are as previously listed.
- Stated that the RP2D and regimen ultimately identified for use in Part 2 of this trial may be comprised of a fixed dose and schedule, a combination of doses to be administered on either a Q1W schedule or a Q2W schedule, or a combination dose and regimen.
- Omitted expansion cohort of patients with fluorodeoxyglucose (FDG)-avid tumors planned to undergo pre- and post-dosing fluorine-18 radiolabeled FDG (¹⁸F-FDG) positron emission tomography (PET) for evaluation of effects of Pan-HER on tumor metabolism.
- Identified populations to be evaluated in 2 of the 4 planned Part 2 dose-expansion cohorts; Cohort A will be a HER2+ solid tumor malignancies Basket Cohort and Cohort B will be pancreatic carcinoma. The composition of Cohort C and Cohort D remains TBD. A protocol amendment detailing all expansion cohorts will follow.
- Increased the number of trial sites and number of patients planned for this trial.
- Modified the washout period between the end of prior therapy and dosing in this trial.
- Specified that patients with primary CNS malignancies are not eligible for participation.

Confidential Page 141 of 156

- Increased the total number of skin biopsies per patient from 2 to 3; the schedule for these procedures has been updated.
- Limited Complement sampling to Part 2 only.
- Clarified timeframes for reporting initial SAEs and follow-up SAE information to the Sponsor or designee are within 24 hours
 of awareness.
- Modified the information to be collected with respect to pregnancies.
- Updated the protocol background to include more recent scientific and clinical experience data.
- Guidelines pertaining to the General Data Protection Regulation have been added.
- Tables and Figure have been updated based on changes described.
- Formatting adjustments, outline modifications, cross-reference link corrections, and other minor typographical corrections and slight wording changes are included.

Refer to **Table 23** for the changes in Protocol Amendment 6.

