5.5 Number of Patients	In total, approximately 131 patients will be included in this trial. It is estimated that approximately 25 patients will be enrolled to receive increasing doses of Pan-HER during Part 1. It is estimated that approximately 6 patients will be enrolled to the PET Expansion Cohort. The exact number of patients will depend upon identification of patients with EDG outdatumers.	In total, approximately 134 patients will be included in this trial. It is estimated that approximately 34 patients will be enrolled to receive increasing doses of Pan-HER during Part 1. Deleted; the PET Expansion Cohort has been removed.
	identification of patients with FDG-avid tumors. It is planned to enroll and treat approximately 100 patients during Part 2: 25 patients in each dose-expansion cohort.	It is planned to enroll and treat approximately 100 patients during Part 2.
6.1 Inclusion Criteria	8. PET Expansion Cohort: Epithelial malignancy, measurable according to RECIST v1.1 that has been confirmed by 18F-FDG-PET imaging to be FDG-avid within 28 days prior to C1/D1 NOTE: Measurable disease is defined as 1 or more target lesions assessed by CT or MRI. A tumor lesion situated in a previously irradiated area is considered measurable only if subsequent disease progression has been documented in the lesion	Deleted; the PET Expansion Cohort has been removed.
	Part 2 ONLY: a. Epithelial malignancy (types to be specified in a CTP amendment), measurable according to RECIST v1.1 that has been confirmed by computed	Part 2 ONLY: a. Epithelial malignancy (HER2+ solid tumor malignancy Basket Cohort, pancreatic carcinoma, and 2 other tumor types to be specified in a protocol

Confidential Page 150 of 156

SECTION	ORIGINAL TEXT	NEW TEXT
	tomography (CT) or magnetic resonance imaging (MRI) within 4 weeks prior to C1/D1	amendment), measurable according to RECIST v1.1 that has been confirmed by CT or MRI within 4 weeks prior to C1/D1
6.2 Exclusion Criteria	1. Any antineoplastic agent (standard or investigational) within 4 weeks prior to C1/D1	1. Any antineoplastic agent for the primary malignancy (standard or investigational) without delayed toxicity within 4 weeks or 5 plasma half-lives, whichever is shortest, prior to C1/D1 except:
		Nitrosoureas and mitomycin C within 6 weeks prior to C1/D1
	6. Central nervous system (CNS) malignancies; known, untreated CNS or	6. Central nervous system (CNS) malignancies including:

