3.2.1 Efficacy Variables

3.2.1.1 Tumor Response according to RECIST v1.1

The anti-tumor activity of Pan-HER will be assessed according to RECIST, v 1.1 using CT or MRI. The use of CT or MRI must be consistent per patient throughout the trial.

Disease Status Evaluation by CT or MRI will occur at:

- Screening

Note: A CT/MRI performed within 28 days prior to Day 1 may be used for evaluation of eligibility and as baseline scan, provided that the CT/MRI has been performed according to the CTP requirements

- End of Cycle 2 and end of every second cycle thereafter, i.e. Cycle 4, 6, 8 etc.

Note: End of cycle assessments may be conducted at any time during the week prior to Day 1 of the next cycle

- After Suspected Progressive Disease (PD) (as soon as possible)
- Confirmation of response, to be performed 28 (+7) days after the first assessment of CR/PR

PAREXEL International
Statistical Analysis Plan Template for Early Phase Studies

Symphogen A/S

Sym013-01

- EOT (if >3 weeks since previous CT/MRI)
- At 1M FUP (if PD was not documented before or at EOT)

If PD is documented at any time, no further disease assessments will be required. Patients with documented PD will be discontinued from Pan-HER so that alternative management of their malignancy may be considered.

For all imaging time points, the following will be recorded as per RECIST v1.1: Target lesions including size, location, and type (nodal/non-nodal); sum of diameters of target lesions; any new lesions noted during trial, including size, location, and type (nodal/non-nodal); response assessment at each visit (PD, SD, PR, CR or Not Evaluable [NE]), per investigators evaluation.

Tumor evaluation according to RECIST 1.1 will be the basis for the derivation of all efficacy endpoints. To be assigned a status of confirmed PR or CR, changes in disease status must be confirmed by repeat imaging studies performed no less than 28 days (4 weeks) after the criteria for response are first met. In the case of SD, follow-up measurements must have met the SD criteria at least once after trial entry at a minimal interval in general no less than 6-8 weeks from first dose of Pan-HER; for the scope of derivation of SD as best overall response, a minimal SD duration of 6 week will be required.

The following anti-tumor response endpoints will be derived based on Tumor evaluation according to RECIST 1.1:

- Target and Non Target Response at each timepoint will be derived according to RECIST 1.1 [1].

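### Since Amendment 6 a short half-life prior therapy may continue after the baseline scan, so change from baseline can mix its effect with that of Pan-HER, in either direction

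*Protocol*

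**What the plan says.** **Baseline scan.** Footnote 11 to Tables 2 and 3 (Protocol 5.3.5) reads "A CT/MRI performed within 28 days prior to C1/D1 can be used for evaluation of eligibility and as baseline scan". Protocol 8.3.1 repeats this, and SAP 3.2.1.1 carries it over as "A CT/MRI performed within 28 days prior to Day 1 may be used for evaluation of eligibility and as baseline scan". The only proviso is that the scan met the protocol's imaging requirements, and 8.3.1 sets none that concerns prior treatment.

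**Washout.** Exclusion 1 (Protocol 6.2) bars antineoplastic agents for the primary malignancy "within 4 weeks or 5 plasma half-lives, whichever is shortest, prior to C1/D1", with a longer limit for "Nitrosoureas and mitomycin C within 6 weeks prior to C1/D1". The Amendment 6 summary (Protocol 21.6) lists the change as "Modified the washout period between the end of prior therapy and dosing in this trial"; the superseded rule was "Any antineoplastic agent (standard or investigational) within 4 weeks prior to C1/D1". The old rule matters here only for telling which patients are concerned.

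**Screening skin biopsy.** Protocol 5.3.1 says "All screening activities must be performed within 14 days prior to C1/D1, unless otherwise specified", and footnote 16 adds "Sample is to be obtained during screening after patient eligibility has been confirmed".

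**Related rules.** SAP 4.2 takes the latest assessment before treatment as baseline. Appendix 1 of the protocol asks that baseline imaging be near treatment start and at most 4 weeks before it. Inclusion 5 requires that treatments of known benefit have been used, but not that the disease progressed on the most recent one.

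**The concern.** Under a flat 4-week washout the two windows matched: a scan recent enough to serve as baseline could not come before the last prior dose. Amendment 6 shortened the washout for short-lived drugs and left the scan window unchanged. A patient can now be scanned, continue a short-lived drug, stop it, and start Pan-HER with the earlier scan as the reference.

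Partial response is a 30% fall from the baseline sum of diameters (Appendix 1; SAP 3.2.1.1). Whatever the tumour does between the scan and C1/D1 is therefore counted in the Pan-HER result. Response is reported by dose level (SAP 4.10.2.1), and a level may hold 3 patients, so one reclassified patient moves that level's response rate by 1/3, or 33 percentage points.

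**Working it through.** The plan states no figure for this point, so there is none to reproduce. The check is window arithmetic.

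**Inputs.** Scan window 28 days (footnote 11, 8.3.1, SAP 3.2.1.1). Washout min(28, 5h) days before C1/D1, where h is the half-life in days (exclusion 1). Biopsy window 14 days (5.3.1). The documents give no half-lives for prior agents, so h is an assumption shown over a range.

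**Longest time the baseline can precede the last prior dose.**
- Scan: 28 − min(28, 5h)
- Skin biopsy: 14 − min(28, 5h), or 0 if negative

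| h (days) | Washout 5h (days) | Scan (days) | Skin biopsy (days) |
|---|---|---|---|
| 0.5 | 2.5 | 25.5 | 11.5 |
| 1 | 5 | 23 | 9 |
| 2 | 10 | 18 | 4 |
| 2.8 | 14 | 14 | 0 |
| 4 | 20 | 8 | 0 |
| 5 | 25 | 3 | 0 |
| 5.6 or more | 28 (4-week limit) | 0 | 0 |

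The thresholds are 28/5 = 5.6 days for the scan and 14/5 = 2.8 days for the biopsy. Under the superseded rule the scan overlap was 28 − 28 = 0. For nitrosoureas and mitomycin C, 6 weeks = 42 days exceeds 28, so there is none.

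**Share of the interval before Pan-HER.** The first response scan falls in the week before Cycle 3, Day 50 to 56. From a scan at Day −28 the interval is 28 + 49 = 77 to 28 + 55 = 83 days, so 28/77 = 36% to 28/83 = 34% of it precedes Pan-HER.

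**Effect on the response threshold.** Suppose the sum changes by a fraction c between the scan and C1/D1 (c is an assumption). Partial response then needs a shrinkage of 1 − 0.7/(1 + c) from the size at C1/D1:
- c = −10%: 1 − 0.7/0.9 = 22.2%
- c = −20%: 1 − 0.7/0.8 = 12.5%
- c = +10%: 1 − 0.7/1.1 = 36.4%
- c = +20%: 1 − 0.7/1.2 = 41.7%

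After growth before C1/D1, the 20% progression criterion needs only 1.2/1.1 − 1 = 9.1% further growth (c = +10%) or 1.2/1.2 − 1 = 0% (c = +20%). The 5 mm absolute rule also applies.

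**Patients concerned.** Protocol 3.2.4.1 counts 19 patients entered as of Amendment 6, which leaves 34 − 19 = 15 of the number planned for Part 1.

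**The case against.** The strongest objections, and what stands of each:

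- **Direction.** A reader might infer that prior-therapy benefit is credited to Pan-HER. The documents do not support that. These patients have no remaining treatment options, so growth before C1/D1 is at least as plausible as shrinkage, and it counts against Pan-HER. The objection stands; the defect is mixing, not a bias of known sign.
- **Confirmation.** Confirmed response needs a repeat scan at least 28 days later, so at scheduled visits it falls no earlier than Day 50 + 28 = 78. This screens out transient carry-over. It does not correct the reference, because the repeat scan is compared with the same baseline. Unconfirmed response, also reported, has no such check.
- **Time to progression.** Its clock starts at the first infusion, and target-lesion progression is judged against the smallest sum on study. Baseline enters only when it is that smallest sum, so this endpoint is affected only in part.
- **Skin biopsy.** It is taken after eligibility is confirmed. Overlap therefore needs the washout to be accepted prospectively, which is possible because it is counted from C1/D1, and a half-life below 2.8 days. If a prior EGFR- or HER-directed drug had already lowered receptor expression, Pan-HER down-modulation would tend to be understated, not inflated.
- **Maxima.** The overlaps are the longest permitted, not expected values, and Appendix 1 already asks for baseline imaging near treatment start. That request discourages long gaps but does not place the scan after the last prior dose.

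**Conclusion.** The gap is real but narrow. For prior agents with a half-life below 5.6 days, the current text permits a baseline scan up to 28 − 5 × half-life days before the last prior dose, and no clause in either document prevents it. Change from baseline, objective response, best overall response and best change in target lesions are exposed.

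Two stronger readings should be resisted. One is that the whole Part 1 efficacy dataset is affected. The 19 patients already entered came in under the flat 4-week rule, and the remaining 15 is a planned number; enrollment was stopped during Part 1, and the documents do not say how many later patients had a short-lived prior agent or an early scan. The other is that the trial's main conclusion is at risk. The Part 1 primary endpoint is dose-limiting toxicity, which does not depend on the baseline scan. Part 2, where response was primary, did not take place, and Part 1 efficacy is descriptive.

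The size rests on assumed half-lives and assumed pre-dose tumour change. Whether any patient is actually affected can be settled only from the collected dates.

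**What to change.** **Timing clause.** In footnote 11 of Tables 2 and 3, Protocol 8.3.1 and SAP 3.2.1.1, accept a scan as baseline only if it was done within 28 days before C1/D1 and after the last dose of prior antineoplastic therapy. The washout itself need not change.

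**Patients already enrolled.** With enrollment stopped, this is the part that helps this trial. Use the prior-treatment dates collected at screening and C1/D1 (Protocol 8.1.5) to flag anyone whose baseline scan or skin biopsy precedes the last prior dose. Show objective response, best overall response, best change in target lesions and the skin results with and without the flagged patients. If nobody is flagged, one sentence in the study report closes the point.

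**Cost.** One clause and one derived flag; the SAP already plans listings of prior systemic therapy and target-lesion assessments. The downside is that some early routine scans could not be reused, or the screening scan would have to be timed later.
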